recommending a minimum of 30 minutes of moderate to vigorous aerobic exercise three times weekly to reduce cardiovascular risk factors. However this recommendation does not include all AIS classifications, people at the age of 65+ or people with an acute SCI due to the lack of sufficient evidence . [15] [16] [17]. However an increased amount of PA in newly injured people with SCI is associated with more favorable lipid profiles and increased VO₂peak during and after discharge from primary rehabilitation [18]. Changes in physical capacity during primary rehabilitation and the years after discharge has previously been described with an increase in VO₂peak of 24% during the early phase of rehabilitation, and with a further increase one year after discharge. Koppenhagen et al found that VO₂peak, despite different trajectories, increased over all in 88% of the participants during a period of 5 years [19, 20]. The course of VO₂peak during and after discharge from primary rehabilitation in a Danish context is not known. After discharge from the primary rehabilitation the amount of PA in people with SCI is varying and 50- 63 % indicates to participate in little or no sports activity on a weekly basis. The majority of those who are physical active are active at mild to moderate intensity (54% and 68% respectively) [10, 15]. Intra- and extra personal factors are influencing participation in PA, including self-efficacy related to being physically active [21]. Therefore a new paradigm is focusing on avoiding inactivity [15]. The amount and intensity of PA in people with SCI in a Danish setting is not known. An association between self-reported PA and adherence to national nutritional guidelines is not necessarily present, and therefore focus on both elements is necessary during lifestyle changes [22].

Prevention and treatment of cardiovascular risk factors

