Although health promotion related to weight, diet, smoking, alcohol intake and physical activity is part of the usual rehabilitation in CSCI, a systematic approach, follow up and feedback is not provided. Assessment of metabolic profile, body composition and physical capacity is not part of the usual care. In the masterplan for patient care at CSCI, health promoting initiatives are described as "communication and conversation with a health promoting purpose with the patient on a daily basis". How the communication is carried out in practice, and whether some health care professionals have a particular responsibility or expertise related to certain aspects of health promotion eg. based on tests or assessments of health, is unclear and not described in detail. A well described and systematic approach related to health care promotion may ensure that all patients at CSCI receive information and knowledge related to health promotion and the risk of cardiovascular disease.

Sub projects

The project consists of a prospective national survey in collaboration with Spinal Cord Injury Centre of Western Denmark and an intervention at CSCI (see the timeline), which results in 4 sub projects

Sub project 1. Prospective representative national survey of Body Mass Index.

This study includes all patients with a new SCI hospitalized at CSCI or Spinal Cord Injury Center of Western Denmark during a period of 9 months whereby 100 patients are expected to participate. On the basis of usual rehabilitation today, data concerning BMI, level of functioning (SCIM III) and neurological status (ISNCSCI) are collected at admission and discharge. At CSCI BMI is collected every 6 weeks. Also the data for quality of life (QoL SCI), depression (PHQ-2), PA (LTPAQ-SCI) and self-assessed ability to be physically active (ESES) will be collected during this period and at follow up 6 months after discharge. A VO₂peak test at discharge is performed and in some patients measurements of accelerometry (AH) will be performed. Patients with a new SCI who are admitted for rehabilitation several months after the time of injury are also included in the prospective survey. Therefore the data for BMI at the time of injury is collected for all patients at admission to primary rehabilitation from both the patient journal and also by asking the patient about weight and height at the time of injury. Data from this subproject serves as a historic control in the Ph.D project.

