Sub project 2. A systematic interdisciplinary multimodal intervention which, as a part of usual care, facilitates PA, healthy diet and maintenance after discharge through strategic patient education, with the aim of decreasing cardiovascular risk factors.

This pre- post study includes all patients with a new SCI who are admitted at CSCI during a period of 12- 18 months including follow up. Complete data sets from admission to follow up is expected for approximately 50-60 patients during this period. The multimodal, interdisciplinary, patient activating and patient supportive intervention will be a part of usual care during the project period, and all newly injured patients will receive all the multimodal components, or parts of them, dependent on eg. the level of injury. Rehabilitation of the physical level of functioning and physical capacity will take place unchanged as usual.

A central part of the intervention is to create a uniform and systematic approach when the patients receive information and instructions about cardiovascular risk factors, PA and a healthy diet through targeted strategic patient education, which includes targeted, individualized and systematic, face- to-face interaction between patients and health care professionals, while working towards, and improving a specific health related outcome through adherence to the working processes, medicine and lifestyle. The concept has been used previously for patient education and prophylaxis of catheter related sepsis [44]. Strategic patient education is carried out by all the health care professions in different settings with a focus on clarifying the importance of PA and a healthy diet. This will take place during the individual functional training and rehabilitation in general, and in conjunction with feedback about outcome measures and tests with subsequent instructions. Strategic patient education will also be integrated as a concept in the education of the interdisciplinary health care professionals and mentors with a SCI, as they will be implementing the content of the education into a daily clinical setting.

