This study includes a subsample of 20 patients participating in subproject 1. The equipment used for monitoring amount and intensity of PA consists of sensors registering acceleration and heart rate and is placed on the thorax of the participant with two surface electrodes. The equipment has previously been used in wheelchair dependent people with SCI, although the reliability of the equipment has not previously been assessed [35]. The precision of the equipment is higher when calibrated individually to the participant using an exercise test [68]. In this project individual calibration will be made during the exercise test described in subproject 3, and continuous measurements of amount and intensity of PA will be made during a period of 24 hours. The test-retest is performed at discharge, separated by 48 hours or within maximum 5 days at the same time of the day.

Outcome measures

All outcome measures will be collected at admission, discharge and follow-up 6 months after discharge. At CSC data for BMI is also collected every 6th week during the hospitalization period.

Primary outcome

Oxygen uptake: Is measured as VO₂peak during a maximal exercise test and is gold standard for measuring aerobic capacity. For people with a SCI several test protocols have been used [36]. The test in this project is performed by using the integrated test protocol in the software of NuStep XR5 or SCI FIT Pro 1. Gradual increments in workload is added every minute depending on the level of lesion. The participant maintains a fixed cadence until predefined criteria for VO₂peak is reached after 8-12 minutes. If VO₂peak is not reached during this period the workload increases each minute until VO₂peak [36, 67]

Secondary outcomes

Objective physical activity: Is measured in a sub-sample in the historic control cohort and the participants in the intervention study with a multisensor device (Actiheart®) recording accelerations and heart rate. It is previously used for wheelchair users with a SCI and individual calibration is important to get the most accurate data [29].

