Data from the patient journals in Epic and the different outcome measures used, is stored in a web based database (Redcap) which is created by the regional Centre for IT, Medico and Telephony (CIMT), with limited access and ID- code, to which pseudo anonymized data is transferred directly,

or via an encrypted USB-stick. An identification list is stored in a locked cabinet at CSCI, local 3403.

Data is stored until December 31, 2027 after which paper material is shredded and data files are deleted.

Statistics

The intervention study and follow up is performed as a pragmatic study and includes, with a few exceptions, all newly injured patients with SCI admitted to primary highly specialized rehabilitation at CSCI. Patients will be included during a time period of 18 corresponding to approximately 40 – 60 patients. Due to the rareness of the morbidity a power calculation is not performed for the primary outcome prior to the intervention, but it is assumed that the total participant number in the intervention and in the historic control cohort, will be comparable to the existing scientific literature.

Numeric continuous data collected at admission, discharge and follow up is reported descriptively as mean and standard deviation together with 95% confidence intervals, or as median, upper and lower quartile as well as interquartile range. Changes over time is reported on the basis of paired t-test. In subproject 3 and 4 the reliability of the outcome measures is analyzed by paired t-test, Pearsons product moment correlation and coefficient of variation or Intraclass correlation coefficient between the test- retest sessions.

Participants, inclusion- and exclusion criteria

Inclusion criteria: All newly injured patients within the previous 12 months, with a SCI and admitted at CSCI are included, regardless of age, neurological level of lesion and completeness of the injury. In subproject 1 all newly injured people with SCI admitted at VCR are also included. Patients under the age of 18 will participate if informed consent is retrieved from their parents.

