Exclusion criteria: Insufficient skills in Danish language and reduced mental function that prevents reading and answering the questionnaires. For the VO₂peak test: Motor complete SCI (AIS A and B) at C4 level or above and assisted ventilatory function. Other exclusion criteria are the presence of decubitus, severe spasticity or musculoskeletal problems considered at risk of aggravation during testing or preventing completion of the test.

Recruitment of participants:

All newly injured patients who are admitted for rehabilitation at CSCI during the project period are included in the intervention (subproject 2) as it becomes a part of usual care during the project period. The Ph.D student is informed about new and future admissions at CSCI by local patient lists every week, and LTPAQ-SCI, ESES, QoL_SCI and NORMON is handed out to the patient and collected again by the Ph.D student. Date and time for the VO₂peak test is handed to the patients physiotherapist, who will make sure to enter it into the patients weekly schedule. The same procedure is repeated at discharge except that QoL_SCI is collected as a part of existing procedures and PHQ-2 is collected by the Ph.D student. In subproject 1, data for VO₂peak at CSCI will only be collected at discharge. All newly injured patients who are admitted for rehabilitation at VCR in the same period are recruited for subproject 1 and data for BMI, SCIM III and ISNCSCI is collected as a part of existing procedures in usual care.

The coordination related to booking of the DEXA-scan and transportation for this is managed by the secretaries. Ordination of the DEXA-scan as well as blood samples related to metabolic profile is handled by the doctors.

Ethical considerations

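### Sub study 2's primary outcome, VO₂peak, has no deciding contrast, and the only test stated for change cannot use the historic control or separate the programme from expected recovery

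*Protocol*

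**What the plan says.** Under Outcome measures, Primary outcome, the protocol lists oxygen uptake, which "Is measured as VO₂peak during a maximal exercise test and is gold standard for measuring aerobic capacity". No visit, change score or comparison is attached. The opening line of Outcome measures gives the schedule: "All outcome measures will be collected at admission, discharge and follow-up 6 months after discharge". In Statistics, the only sentence on testing change is "Changes over time is reported on the basis of paired t-test".

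The design of sub study 2 is described in two ways. The Designs list calls it a controlled intervention study, while Sub project 2 begins "This pre- post study includes all patients with a new SCI who are admitted at CSCI during a period of 12- 18 months including follow". The control is sub study 1, of which Sub project 1 says "Data from this subproject serves as a historic control in the Ph.D project". Recruitment of participants restricts what that control can supply: "In subproject 1, data for VO₂peak at CSCI will only be collected at discharge". Sub project 1 agrees with this, so the general three-visit schedule does not apply to the controls' VO₂peak.

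On the expected course of the outcome, the Background (Impact of physical activity on health and fitness) cites "an increase in VO₂peak of 24% during the early phase of rehabilitation, and with a further increase one year after discharge".

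**The concern.** A paired t-test needs two visits, and the plan has three without saying which pair carries the primary result. The three changes answer different questions: admission to discharge covers the inpatient stay, discharge to follow-up covers maintenance, and admission to follow-up covers both. The Hypothesis refers to both risk reduction and maintenance after discharge, so it does not choose among them.

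The larger difficulty is what a significant result would mean. The one named test works within the intervention cohort, and the protocol's own Background expects VO₂peak to rise there in any case. The plan as written can therefore return a significant primary change when the programme has done nothing. The contrast most likely to be significant, admission to discharge, is the one least able to show an effect. The historic control, which is the reason for calling the study controlled, has no stated role in the analysis of the primary outcome.

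**Working it through.** The protocol states no sample-size calculation, SD or alpha, so there is no figure of its own to reproduce.

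**1. Eligible contrasts.** Three visits give 3 × 2 / 2 = 3 paired contrasts within the intervention cohort. The controls have VO₂peak at discharge only, so they have no paired change, and the cohorts can be compared at that visit alone. Statistics names no test for that comparison. The firm count of stated candidates is three.

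**2. How readily recovery alone gives significance.**
- Inputs from the protocol: about 40 to 60 patients (Statistics) and a cited rise of 24% (Background).
- Assumption: two-sided 5%, in line with the 95% intervals in Statistics.
- From the noncentral t distribution, the paired effect (mean change divided by SD of change) detectable with 80% power is 0.454 at n = 40, 0.404 at n = 50 and 0.368 at n = 60.
- A 24% rise reaches that power when the SD of change, as a share of the baseline mean, is at most 24% divided by the detectable effect:
  - n = 40: 24 / 0.454 = 53%
  - n = 50: 24 / 0.404 = 59%
  - n = 60: 24 / 0.368 = 65%

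The protocol gives no SD, so this is a condition and not a prediction.

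**3. Splitting alpha does not help.** With Bonferroni over three tests (0.05 / 3 = 0.0167), the detectable effects are 0.531 at n = 40 and 0.428 at n = 60. The limits become 24 / 0.531 = 45% and 24 / 0.428 = 56%. Recovery alone would still be detected over a wide range of SDs.

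**4. Family-wise error, and when it applies.** Simulation of 60,000 trials per setting used no true change at any visit, two-sided 5% per test, n = 40 or 60, between-visit correlation 0.5 to 0.9, and compound-symmetric or AR(1) structure. At least one of the three paired tests was significant in 11.7% to 12.6% of trials. For three independent tests the figure would be 1 − 0.95³ = 14.3%.

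That null does not fit the Background:
- If VO₂peak rises to discharge and then holds, the two contrasts from admission are true changes. Only discharge to follow-up is null, with error 5%.
- If VO₂peak also rises after discharge, no paired null is true and no paired test can give a false positive.

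In both cases the significant changes are real changes over time. What would be wrong is attributing them to the programme.

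**The case against.** A separate analysis plan may exist, and hierarchy, alpha split and order of testing are commonly left to it. Their absence is accepted here as no finding. The time point and contrast that define the primary outcome are different: they belong in the protocol, and this protocol's own Statistics section selects a test that excludes the control.

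A reader might infer that three or four full-alpha tests are planned, with a 12% to 16% chance of a false primary result. The documents do not support that. No alpha is stated. The 16% counts a between-cohort test at discharge that Statistics never mentions. Both rates require VO₂peak to change at no visit, which the Background makes unlikely.

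A reader might also infer that success will be declared on whichever contrast is significant. Nothing says so: the study is described as pragmatic, results are reported descriptively with 95% intervals, and there is no decision threshold. The point is that the protocol leaves the choice open, not that misuse is intended.

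The expected rise comes from cited work, and the protocol says that the Danish course of VO₂peak is not known. The 24% therefore indicates direction and possible size, and is no forecast for CSCI. The further rise was cited at one year after discharge, whereas follow-up here is at about 6 months, so the case is weaker for discharge to follow-up than for admission to discharge.

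It can fairly be said that a discharge comparison with historic controls is weak. The controls have no admission VO₂peak, training of physical capacity is to continue unaltered in the intervention period, and a discharge comparison does not test maintenance. All of this stands and limits what the fix can achieve. It remains the only VO₂peak comparison in the protocol that has a control.

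The point concerns sub study 2 only. The primary outcome is listed for the whole project. The link to sub study 2 rests on Statistics, which discusses the primary outcome in relation to the intervention, and on the absence of any paired VO₂peak in the sub study 1 cohort.

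**Conclusion.** The concern holds as a problem of definition and attribution. The primary outcome of sub study 2 has no deciding time point or contrast, and the one stated test of change allows three within-cohort answers and cannot use the historic control. By the protocol's own Background, a significant paired change, above all from admission to discharge, is expected without the programme and cannot support a claim of effect.

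The size is conditional. A rise of 24% would be significant with at least 80% power if the SD of change is below about 53% (n = 40) to 65% (n = 60) of the baseline mean, at an assumed two-sided 5%. If fewer patients can complete the exercise test, these limits fall. Family-wise error of about 12% is a secondary point, confined to the case of no change at any visit.

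**What to change.** In Primary outcome and Statistics, name one deciding contrast for sub study 2: VO₂peak at discharge, intervention cohort against the CSCI historic controls. Report the difference with a two-sided 95% confidence interval, adjusted for data collected in both cohorts, such as neurological level and completeness from the ISNCSCI, preferably as recorded at admission. State that the controls have no admission VO₂peak, so confounding by baseline capacity remains.

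Report the three paired changes as supportive estimates with 95% confidence intervals, and say that they cannot by themselves support a claim of programme effect.

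If the investigators keep a pre-post primary, they should name one paired contrast, describe it as change over time and not as programme effect, and make the other two secondary. The description of sub study 2 as controlled in Designs and as pre-post in Sub project 2 should be reconciled with whichever choice is made.

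The cost is a few sentences in the protocol and an adjusted model in place of a t-test, with no new patients or measurements. The downside is that a significant change on another contrast can no longer be presented as the primary result, and the comparison with historic controls remains non-randomised.

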Pre-intervention education of health care professionals and mentors: Before onset of the intervention, all health care professionals and mentors with a SCI at CSCI will receive information and education about the content and elements of the intervention, cardiovascular risk factors in people with SCI and the effect of PA and healthy diet in order to establish a uniform knowledge at a basic level among all health care professionals and mentors at CSCI as called for in the literature [9]. The sessions are supplemented with evidence based recommendations that can be used by the health care professionals and mentors when they educate the patients. The review by Van Wyk et al emphasizes that patient education is an important part of the interdisciplinary rehabilitation of people with SCI and recommend an individualized approach and the use of different settings in which the patient can receive the education.

Therefore the intervention will include an increased focus on cardiovascular risk factors and systematization of the existing setting and treatment interventions including education of patients- and their relatives in different in different types of forums [45, 46]. New interventions are introduced and several of the outcome measures at admission, discharge and follow up 6 months after discharge are a part of the intervention to facilitate PA and healthy diet through strategic patient education including body weight, body composition, metabolic profile, physical capacity, physical activity, self- assessed ability to be physically active and diet. Also included are instruction and information about PA and the intensity of this by using ratings of perceived exertion, identification of activity and participation problems related to PA and healthy diet using the Canadian Occupational Performance Measure, information about the recommended amount and composition of food on a plate at the lunch and evening servings but also in conjunction with kitchen training and grocery shopping with the occupational therapists. A motivational conversation, tools for decision making, and use of mentors with SCI to facilitate PA and healthy diet are also introduced.

Patient adherence to the elements of the intervention is described descriptively by registration of their participation in the different elements in which they are expected to participate. The adherence of the interdisciplinary health care professionals in relation to the intervention is

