Measure for a varied and healthy diet in an appropriate amount	Questionnaire	Ph.D student	-	X

*1-2 weeks after admission and before discharge Follow up approx. 6 months after discharge.

** Is handled by physiotherapists with knowledge and skills after the project.

Is handled by the Ph.D student at discharge and admission for depression and quality of life respectively.

Subproject 3. Test- retest reliability of a VO2 peak test

This study includes all patients participating in subproject 1 who are able of performing the test. A seated cross-trainer is used (NuStep T5XR) with an incorporated test protocol in the equipment software. Equipment and protocol is reliable in people with traumatic brain injury and has been validated in healthy persons [32, 33]. In people with an incomplete SCI the equipment is safe, and involves a large amount of muscle mass ensuring completion of the test [34]. The equipment may also be used by patients with a complete SCI of the lower extremities, but in case the equipment is difficult to use for people with a complete tetraplegia, an armcranking ergometer will be used (SCI FIT Pro1). The reliability of the cross-trainer has not previously been evaluated in people with SCI. The test- retest study takes place at discharge, separated by 48 hours or within maximum 5 days at the same time of the day. The participants refrain from caffeine, alcohol and intensive physical exercise on the day of testing as well as tobacco smoking to hours before the test. Bladder emptying is taken care off before the test.

Subproject 4. Test-retest reliability of a multi sensor accelerometer.

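### The reliability analysis fixed for sub studies 3 and 4 can be carried out in full without reporting any random retest error

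*Protocol*

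**What the plan says.** The Statistics section of the protocol states of subprojects 3 and 4 that "the reliability of the outcome measures is analyzed by paired t-test, Pearsons product moment correlation and coefficient of variation or Intraclass correlation coefficient", comparing the two sessions. The sentence can be read as t-test and r, plus either CV or ICC, or as t-test, r and CV together, or else ICC. On both readings CV may be omitted. The protocol nowhere names a standard error of measurement (SEM), a within-subject SD, limits of agreement or a smallest detectable change.

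The same section describes numeric data at admission, discharge and follow-up by mean and SD "or as median, upper and lower quartile as well as interquartile range", so session SDs are not guaranteed either.

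On the setting, Subproject 3 says: "This study includes all patients participating in subproject 1 who are able of performing the test". The inclusion criteria admit new injuries "regardless of age, neurological level of lesion and completeness of the injury". The exclusion criteria for the VO₂peak test remove motor-complete injury at C4 or above, assisted ventilation, and some skin, spasticity and musculoskeletal problems. Subproject 3 gives its reason for existing: "The reliability of the cross-trainer has not previously been evaluated in people with SCI". Subproject 4 takes a subsample of 20 patients.

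**The concern.** A reliability study should answer two questions: how far two measurements on the same unchanged person differ, and how that error compares with differences between people. The listed t-test and r answer neither. The ICC answers the second. The within-subject CV answers the first, but only as a percentage of the mean. Treating CV and ICC as alternatives means that the first question can go unanswered while the plan is followed to the letter.

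This matters because sub study 3 is the planned evidence, in people with spinal cord injury, for the equipment behind the primary outcome, VO₂peak. The measurements are also used with individual patients. Sub project 2 says that "several of the outcome measures at admission, discharge and follow up 6 months after discharge are a part of the intervention" and that patient education takes place "in conjunction with feedback about outcome measures and tests with subsequent instructions". Staff who discuss one person's two results need to know how far they would differ by chance. An r, a p-value and an ICC do not tell them.

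**Working it through.** The protocol states no ICC, SD, error or sample size justification for sub studies 3 and 4, so there is no figure to reproduce. What follows is illustration. From the protocol: n = 20 in sub study 4, and a cited VO₂peak gain "of 24% during the early phase of rehabilitation" (section on the impact of physical activity). All SDs, CVs and coefficients below are assumptions.

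**1. Same ICC, different error (no shift, so r = ICC).**
- ICC = SB² / (SB² + SEM²), where SB is the between-subject SD. Hence within-subject CV = between-subject CV × √((1 − ICC)/ICC).
- At ICC 0.90 the factor is √(0.10/0.90) = 0.333.
- Minimal detectable change for one person (95%) = 1.96 × √2 × CV = 2.772 × CV.

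| Between-subject CV (assumed) | Within-subject CV | Minimal detectable change, % of mean |
|---|---|---|
| 20% | 6.7% | 18.5% |
| 30% | 10.0% | 27.7% |
| 50% | 16.7% | 46.2% |

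For scale only, the cited gain of 24% lies outside retest error in the first row and inside it in the other two. It is a group figure, and the protocol sets no individual threshold.

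**2. The same in units.** With r = 0.90 and SEM = total SD × √(1 − r), a total SD of 3, 5 or 8 gives SEM 0.95, 1.58 or 2.53. The limits of agreement (± 1.96 × √2 × SEM) are ± 2.6, ± 4.4 or ± 7.0.

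**3. Same error, wider spread.** Start at ICC 0.70 with SB = 1. The error variance is 0.30/0.70 = 0.4286, SEM is 0.655, and the minimal detectable change is 2.772 × 0.655 = 1.81. Hold that error and widen SB:
- SB = 1.5: 2.25/(2.25 + 0.4286) = 0.84
- SB = 2: 4/(4 + 0.4286) = 0.90

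Both r and ICC rise while the detectable change stays at 1.81.

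**4. What r and the t-test miss.**
- Shift: with SB = 5 and SEM = 1, r = 25/26 = 0.962 whatever the fixed shift between sessions. The absolute-agreement ICC is 25/(26 + shift²/2): 0.962 with no shift, 25/28 = 0.893 with a shift of 2, and 25/34 = 0.735 with a shift of 4.
- Noise: with n = 20 and two-sided 5%, the t-test's power for a true shift of 1 unit is 85% at SEM 1, 32% at SEM 2 and 17% at SEM 3 (noncentral t, SD of differences = √2 × SEM). A noisier device is more likely to show no significant difference.

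**5. Can the error be recovered?** If the mean difference and t are published, SD of differences = |mean difference| × √n / |t|, and SEM = that / √2. This fails if only a p-value or a statement of non-significance is given, and it is imprecise when the mean difference rounds to nearly zero.

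**The case against.** The strongest reply is that reliability detail usually belongs in a statistical analysis plan, which may exist, and that the protocol does name both standard indices. A paired comparison for systematic shift is normal, and the protocol never says that a non-significant t-test or a high r will be taken as proof of reliability. All of that is fair. What stands is that the protocol itself fixes a list, and that list can be completed without any random error. The unstated ICC form alone would be detail for later; the optional error is not.

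The ICC comes from much the same kind of patient as in sub study 2, so it is representative rather than artificial, and the VO₂peak exclusions narrow the spread. This also stands. The spread remains broad, however, and a representative ICC still does not give the size of the error.

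A reader might infer more than the documents support:
- **That reliability would go unmeasured.** It would not. One of CV and ICC is always reported, the set would expose a large shift or a low correlation, and the error is sometimes recoverable as in step 5.
- **That choosing CV settles the matter.** CV is a percentage, so the error in units is still not required.
- **That sub study 2 is biased or patients are misclassified.** Its group mean change is not biased by how reliability is summarised, and no rule labels a patient as changed or unchanged.
- **That sub study 4 must match weekday with weekday.** Subproject 4 matches clock time only, so its window of 48 hours to 5 days permits recordings on different types of day. That activity differs by day type is an inference from a questionnaire instruction mentioning the weekly schedule. The effect is of unknown size, and matching could cost pairs out of only 20.

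**Conclusion.** The point holds as a weakness in what the protocol fixes. If the ICC is chosen, no retest error, relative or absolute, must be reported; if CV is chosen, only a relative one. The practical size depends on a spread that the protocol does not give. Over an assumed between-subject CV of 20% to 50%, the same ICC of 0.90 covers a within-subject CV from 6.7% to 16.7%, a factor of 2.5. This assumes no systematic shift and equal variance in the two sessions.

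The consequence is confined to what the reliability studies can tell their users. It should be corrected, because the better analysis needs only data already to be collected.

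**What to change.** Replace the list in Statistics with wording such as: *Reliability in sub studies 3 and 4 is summarised by the two-way, absolute-agreement, single-measure intraclass correlation coefficient with 95% CI. The mean difference between sessions with 95% CI, and the SEM (within-subject SD) or 95% limits of agreement in measurement units, are always reported beside it. The coefficient of variation is added if the error grows with the mean. The paired t-test is used only as a check for systematic shift. Pearson's correlation is not used as a reliability index.*

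In sub study 4, at most record the type of day of each recording and describe it; matching should not be required.

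The cost is a few sentences and a little more analysis, with no new tests or patients. The headline coefficient may be slightly lower, because an absolute-agreement ICC counts a shift that r ignores.
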